#### 3.2 Secondary Endpoints

- 3.2.1** Toxicity will be classified and graded according to the National Cancer Institute's Common Terminology Criteria for Adverse Events (CTCAE, version 5.0).
- 3.2.2** Progression-free survival (PFS) is defined from the date of initiating study treatment to the date of disease progression per the [International Primary CNS Lymphoma Collaborative Group response assessment criteria](#) [37] or death as a result of any cause.
- 3.2.3** Complete Response (CR) is defined using the [International Primary CNS Lymphoma Collaborative Group response assessment criteria](#) for primary CNS lymphoma [37].
- 3.2.4** Duration of response (DoR) is defined as time from documentation of tumor response to disease progression according to the [International Primary CNS Lymphoma Collaborative Group response assessment criteria](#) [37].
- 3.2.5** OS will be measured from the date of initiating study treatment to the date of death or 5 years (whichever is first). Subjects who have not died by the analysis data cut-off date will be censored at their last date of contact.

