## **5.4 Duration of Therapy**

In the absence of treatment delays due to adverse events, treatment may continue until:

- Disease progression
- Inter-current illness that prevents further administration of treatment
- Unacceptable adverse event(s)
- Pregnancy
- Subject decides to withdraw from study treatment,
- General or specific changes in the subject's condition render the subject unacceptable for further treatment in the judgment of the investigator, or
- Subject is lost to follow up

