(2) Some patients will have a small but persistent enhancing abnormality on MRI related to biopsy or focal hemorrhage. It is often difficult to ascertain whether this represents a residual nidus of tumor or scar tissue. Adjunctive radiologic studies such as single-photon emission computed tomography or positron emission tomography may be helpful, but often the nature of these abnormalities may only be determined by observing the patient with serial scans. If the type of abnormality does not change or slowly involutes over time without therapy and corticosteroids, it is reasonable to categorize it as a CR.

(3) Patients with a persistent minor abnormality on follow-up ophthalmologic examination (persistent non-malignant cells in the vitreous, alteration of the retina/optic nerve that is not consistent with tumor infiltration) may be considered a CRu if this abnormality is unlikely to represent ocular lymphoma.

*Partial response (PR) requires all of the following:*

(1) A  $\geq 50\%$  decrease in the contrast-enhancing lesion seen on MRI as compared with baseline imaging.

(2) Corticosteroid dose is irrelevant to the determination of PR.

(3) Ophthalmologic examination should show a decrease in the vitreous cell count or retinal/optic nerve cellular infiltrate but may continue to show persistent malignant or suspicious cells. Color photos of the posterior pole of the eye should be obtained to document improvement in retinal/optic nerve infiltrates.

(4) No new sites of disease.

Stable disease is defined as less than a PR but is not progressive disease.

*Progressive disease requires the following:*

(1) A more than 25% increase in the contrast-enhancing lesion seen on MRI as compared with baseline or best response (comparison should be made to the smallest of multiple lesions).

(2) Progression of ocular disease as indicated by an increase in the vitreous cell count or progressive retinal or optic nerve infiltration.

(3) Appearance of any new lesion or site of disease (ocular, leptomeningeal or systemic) during or at the end of therapy.

*Relapsed disease (only applicable to patients with a prior CR, CRu) requires the following:*

(1) Appearance of any new lesion.

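### Progression item 1 in Section 8.4.1 compares only the smallest of several lesions, so growth of a larger lesion is missed and one scan can be both partial response and progression

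*Combined protocol and SAP*

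**What the plan says.** Section 8.4.1 gives three items for progressive disease.

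- Item 1 is MRI growth: a rise of more than 25% in the enhancing lesion "as compared with baseline or best response (comparison should be made to the smallest of multiple lesions".
- Item 2 is ocular: "Progression of ocular disease as indicated by an increase in the vitreous cell count or progressive retinal or optic nerve infiltration".
- Item 3 is new disease: "Appearance of any new lesion or site of disease (ocular, leptomeningeal or systemic) during or at the end of therapy".

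Partial response, item 1, needs a fall of at least 50% in the "contrast-enhancing lesion seen on MRI as compared with baseline imaging". It does not mention the smallest lesion. Complete response covers every enhancing abnormality. Relapse after CR or CRu needs a new lesion and uses no percentage.

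Section 8.4.1 states no metric (diameter, area or volume), minimum lesion size, confirmatory scan, or rule for a scan that meets both PR and PD.

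These categories feed the endpoints. ORR at 2 months (3.1), PFS (3.2.2) and DoR (3.2.4) all use the same criteria. PFS "is defined from the date of initiating study treatment to the date of disease progression" or death from any cause. Section 5.4 lists "Disease progression" among the reasons that end treatment, and footnote 14 of the Section 8.1 table says the same in substance.

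**The concern.** With several lesions, item 1 makes the smallest one decide. That has three consequences:

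- **Missed progression.** A dominant lesion can grow without meeting item 1 if the smallest lesion is unchanged. Items 2 and 3 do not cover growth of an existing brain lesion, so the PFS or DoR event is dated late.
- **Early progression.** A fixed percentage of a small lesion is a small absolute change, so a measurement difference can be recorded as an event.
- **Double classification.** PR and PD look at different lesions, so both can be met on one scan. Stable disease is defined to exclude both, but nothing orders PR against PD. Two readers could classify the same scan differently, and at the 2-month scan that choice would decide whether the subject counts as a responder.

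**Working it through.** **1. The plan's own figure.** The only reproducible design figure is the ORR rule in Section 10.2: 10 or more responders of 15. Exact binomial: P(X ≥ 10 | 15, 0.70) = 0.7216 (stated 72%) and P(X ≥ 10 | 15, 0.50) = 0.1509 (stated 0.15). It reproduces and does not depend on the progression wording.

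**2. Literal reading on invented scans (two lesions, diameters, no new or ocular disease).**

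| Scan | Larger lesion | Smallest lesion | PR item 1 | PD item 1 |
|---|---|---|---|---|
| A | 40 → 80 mm | 5 → 5 mm | no | no (0%) |
| B | 40 → 16 mm (−60%) | 5 → 6.3 mm (+26%) | yes, if the larger lesion is read | yes |

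Scan A meets none of the three progression items. Scan B meets PR and PD.

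**3. Effect of the unstated metric.** A 25% rise on a 5 mm lesion is 5 × 0.25 = 1.25 mm if diameter is meant, 5 × (1.25^(1/2) − 1) = 0.59 mm if area, and 5 × (1.25^(1/3) − 1) = 0.39 mm if volume. The 50% cut for PR equals a diameter fall of 50%, 1 − 0.5^(1/2) = 29%, or 1 − 0.5^(1/3) = 21%.

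**4. False calls in an unchanged lesion (illustration).** Lesion size d and reading SD s are assumptions; the documents give neither. With independent normal errors, a later reading Y exceeds 1.25 times the reference X with probability 1 − Φ(z), where z = 0.25d / (s × √(1 + 1.25²)) = 0.25d / (1.601s). The three-scan column is a simulation (at least 300,000 subjects) of C3D1, C5D1 and C7D1, each judged against the smallest earlier reading.

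| d, s (diameter) | z | One comparison | Three scans |
|---|---|---|---|
| 5 mm, 0.25 mm | 3.12 | 0.1% | 0.5% |
| 5 mm, 0.5 mm | 1.56 | 5.9% | 24% |
| 5 mm, 1.0 mm | 0.78 | 22% | 65% |
| 10 mm, 0.5 mm | 3.12 | 0.1% | 0.5% |

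If area is meant, the three 5 mm rows become 5.8%, 22% and 35% for one comparison, and 24%, 64% and 84% over three scans.

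The 25% threshold equals the 95% limit for the difference of two readings when the coefficient of variation is ln(1.25) / (1.96 × √2) = 0.2231 / 2.772 = 8%. At 5% a false call has probability about 0.1% per comparison; at 10% it is about 6%.

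**5. Reach into ORR.** C3D1 is day 57 (2 × 28 + 1) and is the only scheduled follow-up MRI by 2 months, so only the one-comparison column could bear on ORR, and only if PD overrides PR. As an illustration, if 5% or 10% of responders were lost this way at a true ORR of 0.70, the observed rate would be 0.70 × 0.95 = 0.665 or 0.70 × 0.90 = 0.63, and P(X ≥ 10 | 15) would fall from 72% to 61% or 50%. The documents support neither loss rate.

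**The case against.** The strongest reply has five parts.

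- **Other routes to an event.** New lesions and ocular progression also count as progression, death counts for PFS, and relapse after CR or CRu ignores the percentage. This stands, and it limits the effect to events decided by item 1 in subjects with more than one lesion.
- **No measured error.** A reader might infer that 25% is about the size of MRI reading error, so that PFS, DoR and stopping for progression rest on noise. The documents do not support that. They contain no reading error or lesion sizes, and the false-call rate runs from negligible to large across plausible assumptions.
- **Adopted criteria.** The section presents the International Primary CNS Lymphoma Collaborative Group criteria rather than a rule made for this trial. The source cannot be checked here. The protocol nevertheless prints this wording as the rule to be applied, so citing the source does not resolve its ambiguity.
- **Ambiguous bracket.** It follows directly on the baseline or best-response reference and may have been meant as the smallest earlier value. The list also does not say whether any or all items are required. The working treats the items as alternatives. This tempers the literal reading but is itself a reason to clarify.
- **Descriptive endpoints.** PFS and DoR are secondary and carry no test (10.3). This stands and lowers the severity.

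**Conclusion.** The point holds at moderate severity. As written, item 1 does not register growth of a larger existing lesion, can register a trivial change in the smallest, and allows one scan to be both PR and PD with no precedence. Those results follow from the text and need no assumption about measurement error, beyond reading the bracket literally.

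The effect on PFS and DoR is misdated events in multi-lesion subjects, in either direction. Its size cannot be given. The 0.1% to 22% per comparison and 0.5% to 65% over three scans apply only to a subject whose smallest lesion is a truly unchanged 5 mm lesion read by diameter with SD 0.25 to 1 mm. They are not rates for the trial population.

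A reader might also infer that the primary analysis is compromised. That does not follow: ORR changes only if PD is taken to override PR, which the documents do not say, and the stated power and type I error are unaffected by the wording itself.

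**What to change.** For classification of ORR, PFS and DoR, amend Section 8.4.1 and the response worksheet to:

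1. remove the smallest-lesion bracket;
2. assess the 50% and 25% cuts on the same set of enhancing lesions, with one stated metric;
3. take the smallest value recorded since baseline as the progression reference;
4. state which category applies when a scan meets both;
5. note in Sections 3.1 and 3.2 any departure from the cited criteria.

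The metric is for the sponsor to choose. Summed areas are one possibility, though not one found in the documents. For unchanged 25 mm and 5 mm lesions with reading SD 0.5 to 1 mm, the false-call rate on the sum is under 0.01% to 2.2% per comparison, against 22% to 35% for the 5 mm lesion alone by area.

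The cost is a short text amendment and no added imaging. The downside is a possible small loss of comparability with results read under the published wording. Existing scans can be re-read, but this cannot fully repair a false call already made: footnote 9 in Section 8.1 continues scans only to progression, and off-treatment MRI (5.5) is for subjects removed before progression, so a later true progression date may not be recoverable. The change is worth more the sooner it is made.

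Because progression also governs treatment duration, Sections 5.4, 8.1 (footnotes 9 and 14) and 8.4.1 must be reconciled. No treatment-stopping rule is proposed here.

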## 9.0 ADVERSE EVENTS

### 9.1 Definitions

#### 9.1.1 Adverse Event (AE)

An adverse event (AE) is any untoward medical occurrence (e.g., an abnormal laboratory finding, symptom, or disease temporally associated with the use of a drug in a subject or clinical investigation subject administered a pharmaceutical product and which does not necessarily have a causal relationship with this treatment. An AE can therefore be any unfavorable and unintended sign (including an abnormal laboratory finding), symptom, or disease temporally associated with the use of a medicinal product, whether or not related to the medicinal product.

Preplanned Hospitalization for elective surgery or routine clinical procedures that are not the result of an AE (e.g., surgical insertion of a central line) need not be considered AEs and should not be recorded as an AE. Disease progression should not be recorded as an AE, unless it is attributable by the investigator to the study therapy. Unplanned diagnostic tests and procedures are not AEs; however, the sign/symptoms leading to them are AEs. Pre-existing conditions (unless they worsen) and abnormal lab values that are judged to be not clinically significant by the investigator are not AEs.

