#### 1.4.2 Adverse Events

An aggregate safety analysis of acalabrutinib monotherapy was conducted in order to assess safety for acalabrutinib-exposed subjects with hematologic malignancies without confounding toxicity from combination therapy drugs. The analysis was performed on a 9-study integrated monotherapy population (hereafter called ‘Mono HemMalig population’), which consisted of treated subjects in 6 acalabrutinib monotherapy studies (ACE-CL-309, 15-H-0016, ACE-CL- 001, ACE-LY-002, ACE-LY-004, and ACE-WM-001) and treated subjects in the acalabrutinib monotherapy treatment arms of 3 additional combination studies (ACE-CL-007, ACE-LY-003 and ACE-MY-001). As of the 30 October 2020 data extraction date, the pooled Mono HemMalig population represented 1079 acalabrutinib-exposed subjects with a median exposure of 28.5 months (range: 0.0 to 65.3 months). On the basis of the analysis of data from this pooled population, the overall safety of acalabrutinib monotherapy in subjects with hematologic malignancies is considered acceptable.

A total of 1052 subjects (97.5%) had at least 1 AE, and over half (650 subjects [60.2%]) had at least one Grade  $\geq 3$  AE. The most commonly reported AEs ( $\geq 20\%$ ) of any grade were diarrhea (37.7%), headache (37.4%), upper respiratory tract infection (26.3%), cough (23.6%), fatigue (23.0%), contusion (22.5%), nausea (22.2%), and arthralgia (21.3%). The most frequently reported Grade  $\geq 3$  AEs ( $\geq$

2%) were neutropenia (12.0%), anemia (7.8%), pneumonia (6.3%), hypertension (3.8%), thrombocytopenia (3.5%), diarrhea (3.0%), syncope (2.4%), and dyspnea (2.0%).

Treatment-related AEs were reported for 792 subjects (73.4%), and 284 subjects (26.3%) had Grade  $\geq 3$  treatment-related AEs. The most frequently reported treatment-related AEs ( $\geq 5\%$ ) of any grade were headache (26.1%), diarrhea (17.9%), contusion (14.5%), neutropenia (9.5%), nausea (8.8%), fatigue (8.6%), arthralgia (6.9%), petechiae (6.0%), and upper respiratory tract infection (5.5%). The most frequently reported treatment-related Grade  $\geq 3$  AE ( $\geq 2\%$ ) was neutropenia (8.5%).

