**Table 2. Acalabrutinib Dose Modifications**

CTCAE Grade	Acalabrutinib Dose Modifications
Hematologic Toxicities	
Neutropenia	
Grade $\leq 3$	No dose modification is required
Grade 4, initial or second occurrence	Hold acalabrutinib until recovery to Grade $\leq 1$ or baseline; may restart at original dose level 
Grade 4, third occurrence	Hold acalabrutinib until recovery to Grade $\leq 1$ or baseline; restart at one dose level lower (100 mg QD) 
Grade 4, fourth occurrence	Discontinue acalabrutinib
Thrombocytopenia	
Grade 1 or 2	No dose modification is required
Grade 4, or Grade 3 in presence of significant bleeding, initial or second occurrence	Interrupt acalabrutinib.  Once toxicity has resolved to Grade 1 or baseline level, acalabrutinib may be resumed at 100 mg approximately every 12 hours.
Grade 4, or Grade 3 in presence of significant bleeding, third occurrence	Interrupt acalabrutinib.  Once toxicity has resolved to Grade 1 or baseline level, acalabrutinib may be resumed at a reduced frequency of 100 mg once daily.
Grade 4, or Grade 3 in presence of significant bleeding, fourth occurrence	Discontinue acalabrutinib
Nonhematologic Toxicities	
Nausea, Vomiting, or Diarrhea	
Grade 1 or 2	No dose modification is required
Grade $\geq 3$ , initial or second occurrence	Interrupt acalabrutinib.

	Once toxicity has resolved to Grade 1 or baseline level, acalabrutinib may be resumed at 100 mg approximately every 12 hours
Grade $\geq 3$ , third occurrence	Interrupt acalabrutinib.  Once toxicity has resolved to Grade 1 or baseline level, acalabrutinib may be resumed at a reduced frequency of 100 mg once daily
Grade $\geq 3$ , fourth occurrence	Discontinue acalabrutinib

 Neutrophil growth factors are permitted per American Society of Clinical Oncology (ASCO) guidelines [38] and use must be recorded on the electronic case report form (eCRF).

As appropriate, certain laboratory abnormalities may warrant more frequent monitoring (e.g., once per week) until abnormalities have recovered to Grade  $\leq 1$ . If the subject tolerates a reduced dose of acalabrutinib for  $\geq 4$  weeks then the dose may be increased to the next higher dose level, at the discretion of the investigator. Such re-escalation may be particularly warranted if further evaluation reveals that the AE that led to the dose reduction was not treatment-related. The maximum dose of acalabrutinib is 100 mg BID.

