#### Footnotes to Time and Events Table

1. All screening assessments should be completed within 28 days before initiating study therapy unless otherwise specified. If screening labs are performed within 72 hours of initiating study treatment on C1D1, they do not need to be repeated. Each scheduled visit should occur within  $\pm 3$  days of the scheduled visit while the subject is receiving study treatment. The end of treatment visit should occur 30 days ( $\pm 7$  days) after discontinuing study therapy and all ongoing AEs should be followed until resolution or the condition has stabilized with no further change expected.
2. Relevant medical history will be recorded at the screening visit. Medical history focused on symptoms / toxicity will be performed thereafter. Medical history includes the collection of clinically significant AEs.
3. A complete physical exam should be conducted at screening i.e., baseline including height (baseline only) and weight. A targeted physical exam including weight should be conducted on Day 1 of each cycle. Vital signs (blood pressure, pulse and temperature) should be obtained at each visit.
4. HBV and HCV testing will be performed during screening. Subjects who are hepatitis B core antibody positive and viral load negative at baseline must receive entecavir prophylaxis. Additionally, these subjects must be monitored for hepatitis b reactivation every before beginning every 4th cycle (Cycles 4, 8...etc.).
5. Hematology should include complete blood count with white blood cell differential.
6. Serum chemistry will include sodium, potassium, chloride, CO2, BUN, creatinine, glucose, calcium, albumin, total protein, total bilirubin, AST, ALT, alkaline phosphatase. LDH will be performed at screening only.
7. International normalized ratio (INR) or prothrombin time (PT) and activated partial thromboplastin time (aPTT) will be performed during screening to ensure eligibility criterion 4.1.9 is met.
8. Serum pregnancy test must be performed in female subjects of childbearing potential within 72 hours before initiating study treatment on day 1 of cycle 1. For subsequent cycles, a pregnancy test will be done on day 1 of odd cycles.

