### 10.3 Data Analysis Plans

Analysis of efficacy will be conducted following pre-specified inference rule on rejecting the null hypothesis:  $H_0: \text{ORR} \leq 50\%$ . Specifically, we will reject the null hypothesis if and only if there are  $>9$  ORs in the 15 subjects. The main analysis is inferential because we frame it as a hypothesis-testing problem. We will also calculate 2-sided 95% clopper-Pearson confidence interval for ORR.

Secondary endpoints include PFS, CR, DoR, overall survival, and safety/toxicity. Analyses of secondary endpoints will be descriptive. Specifically, time-to-event outcomes like PFS, DoR, and OS will be analyzed using Kaplan-Meier method, and Kaplan-Meier survival curves will be provided. Categorical outcomes like CR, and safety/toxicity (different types of AEs) will be summarized using frequencies.

- For the primary outcome, ORR, there should be no missing data. We will replace non-evaluable cases with new subjects so that the total sample size of 15 evaluable subjects is guaranteed.
- There is only one test for the primary endpoint and hence there is no multiplicity issue.

Per exploratory endpoints:

[REDACTED]

[REDACTED]

[REDACTED]

[REDACTED]

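### Laboratory toxicities graded by measured value, mainly Grade 3, can drop out of the descriptive toxicity endpoint: section 9.1.1 sets no CTCAE grade floor and section 10.3 plans only AE frequencies

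*Combined protocol and SAP*

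**What the plan says.** Section 3.2.1 makes toxicity a secondary endpoint: "Toxicity will be classified and graded according to the National Cancer Institute's Common Terminology Criteria for Adverse Events", version 5.0. Sections 5.2 and 8.3 make every subject who takes at least one dose evaluable for it.

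Section 9.1.1 first includes abnormal laboratory findings among adverse events, then takes some out again: "abnormal lab values that are judged to be not clinically significant by the investigator are not AEs". It does not define clinical significance and gives no grade above which a value must be recorded.

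Section 7.1.5 describes what goes on the case report form for each adverse event (dates, grade, outcome, treatment, relation to drug). Section 10.3 gives the whole planned analysis in one sentence: "Categorical outcomes like CR, and safety/toxicity (different types of AEs) will be summarized using frequencies". No table of laboratory values by CTCAE grade is described, although the Time and Events Table schedules hematology at every treatment visit and chemistry at all of them except Cycle 1 Day 8.

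**The concern.** For blood counts and liver tests, the CTCAE grade is set essentially by the measured value. The plan nevertheless places an undefined investigator judgement between that value and the endpoint. A Grade 3 count judged not clinically significant is not an AE, and an analysis that counts AEs will not show it.

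These events matter for this drug. Section 6.1.4 lists Grade 3 or 4 neutropenia, anemia and thrombocytopenia among the important identified risks, and hepatotoxicity as the one important potential risk. In the pooled monotherapy data in section 1.4.2, neutropenia and anemia are the two most frequent AEs of Grade 3 or higher. At stake is whether a pilot of at most 16 subjects describes those events by the scale it says it uses.

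**Working it through.** The plan states no figure on this point to reproduce. The check has two parts: the chain from value to table, and an illustrative size.

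**From value to table**

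1. Endpoint: toxicity, CTCAE v5.0 grade, all dosed subjects (3.2.1, 5.2, 8.3).
2. Definition: a laboratory value judged not clinically significant is not an AE, at any grade (9.1.1).
3. Capture: AEs are recorded with their grade (7.1.5).
4. Analysis: frequencies of types of AE (10.3).

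A value removed at step 2 does not reach step 4. The exemption can only remove laboratory events from the count, so its effect runs one way.

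**Which events are exposed**

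| Laboratory event | What else in the plan marks it | Likely to be lost? |
|---|---|---|
| Grade 4 neutropenia | Hold or discontinuation in Table 2 | No |
| Grade 4 thrombocytopenia, or Grade 3 with significant bleeding | Interruption or discontinuation in Table 2 | No |
| AST or ALT at least 3 x ULN with bilirubin at least 2 x ULN | Hy's law text in 9.2 (possible SAE) | No |
| Grade 3 neutropenia | Named as a risk in 6.1.4; no recording rule | Possible |
| Grade 3 thrombocytopenia without significant bleeding | Named as a risk in 6.1.4; no Table 2 row | Possible |
| Grade 3 anemia | Named as a risk in 6.1.4; no Table 2 row | Possible |
| Isolated AST, ALT or bilirubin elevation | Hepatotoxicity named in 6.1.4; no Table 2 row | Possible |

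Even in the first three rows, no text says that the value must be recorded as an AE whatever the judgement. But an investigator who stops study drug because of a count can hardly call it not clinically significant.

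**Illustrative size**

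Inputs: n = 16 (maximum accrual, section 10.2). Pooled Grade 3 or higher reported-AE rates from section 1.4.2: neutropenia 12.0%, anemia 7.8%, thrombocytopenia 3.5%. Assumption: these rates carry over to this population.

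- Neutropenia: 16 x 0.12 = 1.92 subjects expected; chance of at least one = 1 - 0.88^16 = 87%.
- Anemia: 16 x 0.078 = 1.25; chance of at least one 73%.
- Thrombocytopenia: 16 x 0.035 = 0.56; chance of at least one 43%.

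Let f be the unknown fraction of neutropenia cases judged not clinically significant. The expected number recorded is 1.92 x (1 - f), and the chance of recording none is (1 - 0.12 x (1 - f))^16.

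| f | Expected recorded | Chance of recording none |
|---|---|---|
| 0 | 1.92 | 13% |
| 0.5 | 0.96 | 0.94^16 = 37% |
| 1 | 0 | 100% |

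With so few events, each omission shows. Exact (Clopper-Pearson) 95% intervals are: 2/16 = 12.5% (1.6% to 38.3%); 1/16 = 6.3% (0.2% to 30.2%); 0/16 = 0% (0% to 20.6%).

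The documents give no Grade 3 or higher rate for liver tests, so none is sized here.

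**The case against.** The strongest reply is that the exemption is common wording, defensible on its own, and that the rest of the plan limits what it can do. Toxicity assessment has its own row in the Time and Events Table, and its footnote 15 refers to CTCAE v5.0 with no filter for significance. Sections 5.2 and 8.3 likewise speak of any toxicity. Section 10.3 does not say that laboratory values are excluded; that is inferred from a short parenthesis and from silence. The values are collected on schedule, section 11.4 has the study data entered in OnCore, and a worst-grade table could be produced later. Secondary analyses are descriptive, the ORR test does not use these data, and the data and safety monitoring committee receives safety data separately under section 9.5.

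Most of this stands as a limit on importance. It does not close the gap. The assessment row says how toxicity is graded, but 9.1.1 decides what counts as an AE, and AEs are what 10.3 names for analysis. A table that could be made later is not a planned one.

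Three stronger readings are tempting and are not supported:

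- A reader might take Table 2's "No dose modification is required" for neutropenia up to Grade 3 as permission to call it not clinically significant. The same instruction applies to Grade 1 or 2 nausea, vomiting and diarrhea, which remain AEs, and section 6.1.4 treats Grade 3 cytopenias as a matter for close monitoring.
- A reader might cite footnote 2, "Medical history includes the collection of clinically significant AEs", as a second filter. It belongs to the medical history row, not to toxicity assessment.
- A reader might object that rates would not be comparable between sites. No site comparison is planned.

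**Conclusion.** The concern holds in limited form. As written, the plan allows laboratory events graded by their value to be left out of a CTCAE-graded secondary endpoint, and any resulting error is downward. The exposure is mainly Grade 3 cytopenias without bleeding and isolated liver-test elevations.

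A reader might infer that Grade 3 and 4 events generally will disappear, or that toxicity will in fact be understated by a known amount. The documents support neither. Table 2 and the Hy's law text make loss of the gravest events implausible, and f may be zero. The 12.0% is itself a rate of reported AEs. The documents do not say whether a similar filter applied in those studies, so reducing it further may count the filter twice. It also includes Grade 4 cases, and no split by grade is given. The figure of about 1.9 in 16 therefore shows only that a few subjects could be affected.

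The conclusion assumes that 9.1.1 and 10.3 are followed literally and that no laboratory table is planned beyond what they state. The loss would be from the planned summary, not from the source data. This is a cheap improvement to a descriptive analysis, not a threat to the trial's main result.

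**What to change.** In section 10.3, add beside the AE frequencies a table of the worst post-baseline CTCAE v5.0 grade per treated subject for ANC, platelets, hemoglobin, AST, ALT and bilirubin, computed from the hematology and chemistry values already collected, with the shift from baseline. The shift is needed because section 4.1.9 admits subjects whose baseline values are already abnormal, for example AST or ALT up to 2.5 x ULN.

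Optionally, state in section 9.1.1 that laboratory values of CTCAE Grade 3 or higher are recorded as AEs whatever their judged significance. This is more debatable than the table, since it changes a common exemption and adds AE entries. The table alone removes the dependence on judgement from the summary of these six parameters.

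The cost is one more table, with no extra blood draw and no change to any treatment rule. The reported rates may look less favourable.
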